### 12.7.4. Analyses of Other Efficacy and Exploratory Endpoints

The other efficacy endpoints are provided in Section 6.1.1.3, and exploratory endpoints are provided in Section 6.1.2.

The following endpoints will be analyzed using a mixed-model repeated-measures analysis as described for the primary endpoint (see Section 12.7.1):

- The mean change from baseline over time for eGFR and urine protein excretion, urine albumin excretion, UA/C, and UP/C based on a 24-hour urine sample.

- The mean change from baseline in QoL, measured via PRO at each visit.
- Changes from baseline in blood pressure at each visit.

The change from baseline to 4 weeks post-cessation of randomized treatment (114 weeks) will be analyzed via analysis of covariance. The dependent variable will be the change from pre-treatment baseline eGFR at Week 114, 4 weeks following planned discontinuation of randomized treatment. Fixed effects for randomized treatment and baseline eGFR will be included. The analysis will be stratified by the randomization strata. The treatment effect will be the contrast between sparsentan and irbesartan LS means. The LS means, treatment effect estimate, 95% CI, and p-value will be presented.

Change from baseline in eGFR at 6 weeks post-randomization will be analyzed using analysis of covariance on the change in eGFR from randomization to Week 6; this analysis will be performed to assess the acute effect of randomized treatment. The change in eGFR from randomization to Week 6 will be the dependent variable, with a fixed effect for randomized treatment and baseline eGFR included as a covariate. The analysis will be stratified by the randomization strata. The treatment effect will be the contrast between sparsentan and irbesartan LS means. The LS means, treatment effect estimate, 95% CI, and p-value will be presented. Similarly, the change from EOT in eGFR at 4 weeks following cessation of treatment will be analyzed using analysis of covariance; the dependent variable will be the change from EOT.

The following endpoints, considered as simple binary outcomes, will be analyzed using a logistic regression analysis with a fixed effect for randomized treatment and baseline eGFR included as a covariate. The analysis will be stratified by the randomization strata. The treatment effect estimate from the model will be the contrast between sparsentan and irbesartan log odds. The treatment effect estimate, and its 95% CI will be back-transformed to provide results on the odds ratio scale, and the associated two-sided p-value will be presented as follows:

- The proportion of patients achieving a urinary protein excretion of  $<0.3$  g/day up to Week 110.
- The proportion of patients achieving a urinary protein excretion of  $<1.0$  g/day up to Week 110.
- The proportion of patients requiring systemic immunosuppressive medication during the study.
- The frequency of hospitalizations (for any reason and for reasons related to the kidney).

The proportion of patients reaching a confirmed 40% change from baseline in eGFR, ESRD, or death will be analyzed via PROC PHREG in SAS in terms of the time to the first of a confirmed 40% change from baseline in eGFR, ESRD, or death using a Cox regression model stratified for the randomization stratification factors and with a fixed effect term for randomized treatment. The hazard ratio along with its 95% CI and two-sided p-value will be provided. The data will also be displayed by randomized treatment group using Kaplan-Meier estimates of the cumulative density function.

The use of systemic immunosuppressive medication and the frequency of hospitalizations will also be analyzed in terms of the number of systemic immunosuppressive medications and the

number of hospitalizations for any reason per patient, using a Negative Binomial regression model via PROC GENMOD in SAS. The model will be stratified for the randomization stratification factors and will include a fixed effect term for randomized treatment. The analyses will be adjusted for duration of exposure to randomized treatment. Estimated event rates will be extracted from the model for each randomized treatment. The treatment effect will be presented as the ratio of event rates together with the associated 95% CI and two-sided p-value.

The total duration of hospitalizations for any reason per patient will be further analyzed using analysis of covariance with a fixed effect term for randomized treatment and baseline eGFR included as a covariate. The analysis will be stratified by the randomization factors. The treatment effect will be the contrast between sparsentan and irbesartan LS means. The LS means, treatment effect estimate, 95% CI, and p-value will be presented.

The proportion of patients with hematuria at each visit will be analyzed using a generalized, mixed-model, repeated-measures analysis using PROC GLIMMIX in SAS. Fixed effects will be included for baseline eGFR value (30 mL/min/1.73 m^2 to <60 mL/min/1.73 m^2 and ≥60 mL/min/1.73 m^2) and urine protein excretion (≤1.75 g/day and >1.75 g/day), as well as for randomized treatment, visit, and randomized treatment-by-time interaction. Patient will be included as a random effect. A logit link function will be used with distribution set to binomial. An unstructured covariance matrix will be assumed; if convergence issues arise, a first-order, auto-regressive structure will be used. Treatment effect estimates will be extracted from the model at each visit in terms of the difference between randomized treatments in log odds, together with the associated 95% CI and two-sided p-values. Treatment effects and CIs will be back-transformed to provide results on the odds ratio scale.

## **12.8. Safety Evaluation**

Descriptive statistics will be used to summarize the safety data by randomized treatment group for the double-blind period. All safety evaluations will be conducted based on the Safety Analysis Set. Observed data will be listed by patient.

### **12.8.1. Physical Examination and Vital Signs**

The number and percentage of patients with physical examination abnormalities at each visit will be summarized and presented for each body system. A listing of abnormalities will also be provided. Body weight will be summarized as changes from baseline.

The presence and staging of edema will be summarized by frequency counts and percentages based on semi-quantitative evaluation of edema findings (see [Section 15.2.4](#)). A shift table indicating changes in edema from baseline to each postbaseline visit will be provided.

Vital signs data will be summarized as changes from baseline and will be classified as low, normal, or high based on reference ranges pre-specified in the SAP. Vital sign abnormalities for each treatment will be summarized using shift tables.

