### 7.1. Criteria for the Double-blind Period

#### 7.1.1. Inclusion Criteria for the Double-blind Period

A patient will meet all of the following criteria to be eligible for this study:

1. The patient is willing and able to provide signed informed consent.
2. The patient is male or female, aged  $\geq 18$  years.
3. The patient has biopsy-proven IgAN. The biopsy may have been performed at any time in the past.
4. The patient has a urine protein excretion value  $\geq 1.0$  g/day at screening.
5. The patient has an eGFR value of  $\geq 30$  mL/min/1.73 m^2 at screening.
6. The patient has been on a stable dose of ACEI and/or ARB therapy for at least 12 weeks prior to screening that is:
  - A. the patient's maximum tolerated dose and
  - B. at least one-half of the MLD (see Appendix B, [Section 15.2.3](#) for minimum ACEI/ARB daily dose requirements at screening).
7. In the Investigator's opinion, the patient's blood pressure has been managed in accordance with standard-of-care using ACEI and/or ARB therapy as described in inclusion criterion 6 and additional anti-hypertensive agents if needed. At screening, the patient's systolic blood pressure must be  $\leq 150$  mmHg and diastolic blood pressure must be  $\leq 100$  mmHg.
8. The patient is willing to undergo a change in ACEI and/or ARB and anti-hypertensive medications.
9. Women of childbearing potential (WOCBP), beginning at menarche, must agree to the use of 1 highly reliable (ie, can achieve a failure rate of  $< 1\%$  per year) method of contraception from 7 days prior to the first dose of study medication until 90 days after the last dose of study medication (including open-label sparsentan). Highly reliable contraception methods include stable oral, implanted, transdermal, or injected contraceptive hormones associated with inhibition of ovulation, or an intrauterine device in place for at least 3 months. One additional barrier method must also be used during sexual activity, such as a diaphragm or diaphragm with spermicide (preferred) or male partner's use of male condom or male condom with spermicide (preferred), from Day 1/Randomization until 90 days after the last dose of study medication. WOCBP are defined as those who are fertile, following menarche and until becoming postmenopausal

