### **8.3.2. Dose Modification, Reduction, or Discontinuation**

Patients who display asymptomatic systolic blood pressure values  $\leq 100$  mmHg, diastolic blood pressure values  $\leq 60$  mmHg, or present with clinical symptoms of orthostatic hypotension but otherwise tolerate the initial sparsentan dose will continue after the Week 2 visit (or the Week 116 visit for the open-label extension period) without titrating up to the sparsentan target dose. Patients whose sparsentan dose is not titrated up to the target dose at Week 2 (or Week 116) may titrate up to that dose at any time based on evaluation of the Investigator in consultation with the Medical Monitor as needed.

The KDIGO Clinical Practice Guideline for Glomerulonephritis ([KDIGO 2012](#)) recommends a blood pressure target of  $<125/75$  mmHg when initial proteinuria is  $>1$  g/day. The KDIGO recommendation reflects standard-of-care in the United States (US) and all other participating countries. This is the basis for the 125/75 mmHg blood pressure target in the double-blind period, with the goal of attaining comparable blood pressure levels between treatment groups.

Throughout the study (including the open-label extension period), patients will be maintained on the maximum allowed dose of sparsentan they can tolerate while secondarily maintaining blood pressure as close as possible to the target of 125/75 mmHg. To maintain blood pressure, the Investigator will be encouraged to either treat patients with additional anti-hypertensive agents (with the exception of ACEIs, aldosterone blockers, aliskiren, ARBs, or ERAs) or withdraw anti-hypertensive agents. In the case of intolerable hypotension, withdrawal of additional anti-hypertensive agents should be accomplished before considering withdrawal or dose reduction of study medication. At the discretion of the Investigator, patients may reduce their study medication dose in the double-blind period from 2 capsules/day to 1 capsule/day for safety or tolerability reasons.

Sparsentan doses may be modified (either 200 mg or 400 mg) at any time throughout the open-label extension period for safety or tolerability reasons at the Investigator's discretion.

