### 10.5. Vital Signs

The results and change from baseline to each post-baseline scheduled visits will be summarized for blood pressure (systolic and diastolic), heart rate, respiration rate, temperature, and weight.

The number and percentage of patients meeting the following criteria at any time during the study will also be summarized:

- Systolic blood pressure:
  - $\leq 100$  mmHg
  - A decrease from baseline more than 30 mmHg
  - $>180$  mmHg
  - An increase from baseline more than 40 mmHg
- Diastolic blood pressure:
  - $\leq 60$  mmHg
  - A decrease from baseline more than 20 mmHg
  - $>105$  mmHg
  - An increase from baseline more than 20 mmHg
- Heart rate:
  - $<45$  beats per minute
  - A decrease from baseline more than 20 beats per minute
  - $>120$  beats per minute
  - An increase from baseline more than 20 beats per minute

For the analysis of orthostatic hypotension, the number and percentage of patients with >20 mmHg decrease in systolic blood pressure at any time and the number and percentage of patients with > 10 mmHg decrease in diastolic blood pressure at any time will be presented.

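### SAP 10.5 omits the vital-sign shift tables that Protocol 12.8.1 promises, and no planned blood-pressure row separates new low readings from those present at baseline

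*Protocol*

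**What the plan says.** Protocol 12.8.1 makes two commitments for vital signs. They are to be "classified as low, normal, or high based on reference ranges pre-specified in the SAP", and "Vital sign abnormalities for each treatment will be summarized using shift tables".

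SAP 10.5 summarizes results and change from baseline by visit. It then adds patient counts: "The number and percentage of patients meeting the following criteria at any time during the study will also be summarized". There are twelve criteria. Six are absolute limits: SBP ≤100 or >180 mmHg, DBP ≤60 or >105 mmHg, heart rate <45 or >120 per minute. Six are changes from baseline, such as "A decrease from baseline more than 30 mmHg" for SBP and the corresponding 20 mmHg fall for DBP. Orthostatic falls are counted separately. There is no low/normal/high cross-tabulation against baseline, and respiration rate and temperature have no limits.

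The SAP does specify shift tables for laboratory values (10.4.1, 10.4.2) and peripheral edema (10.6.1). SAP 5.4 declares the analyses consistent with Protocol Amendment 5 and lists clarifications and additions. The missing vital-sign shift tables are not among them.

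Protocol 7.1.1, criterion 7, requires that in the investigator's opinion "blood pressure has been managed in accordance with standard-of-care using ACEI and/or ARB therapy as described in inclusion criterion 6", and caps screening SBP at 150 and DBP at 100 mmHg. It sets no lower limit.

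**The concern.** The protocol's table would show who moved from normal to low. The SAP's absolute rows cannot: a patient who enters at SBP 98 and stays there is counted like one who falls from 125 to 98. Read literally, the time frame also takes in readings before the first dose and the Week 114 reading off study drug.

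The distinction matters because low blood pressure is a plausible difference between the arms. Protocol 4.3 reports a larger pressure reduction with sparsentan 800 mg than with irbesartan 300 mg, and hypotension in 13.7% of sparsentan patients in the earlier FSGS study. SAP 10.1.2 makes hypotension a safety topic of interest. The limits 100 and 60 mmHg are also the trial's own: under Protocol 8.3.2, patients at or below them who otherwise tolerate the initial dose continue "without titrating up to the sparsentan target dose". A table at those limits will be read as evidence of what the drug does.

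**Working it through.** The plan states no figure on this point, so there is none to reproduce. The check has two parts.

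**1. Does another planned output isolate new readings at or below 100/60?**

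- *Falls >30 mmHg (SBP) or >20 mmHg (DBP).* From the protocol's target of 125/75, reaching 100/60 is a fall of 125 − 100 = 25 and 75 − 60 = 15 mmHg. Such a patient is newly low and appears in neither row.
- *Change from baseline by visit, and the blood-pressure MMRM (SAP 8.7.3).* These describe averages. Investigators also adjust antihypertensives toward a common target (Protocol 8.3.2), which tends to narrow mean differences.
- *Orthostatic counts.* These concern postural falls.
- *Hypotension TEAEs (SAP 10.1.2).* These are treatment-emergent, but depend on an event being reported.

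None isolates the new low reading.

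**2. What does counting baseline-low patients do to the comparison?**

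Inputs from the documents: about 380 patients randomized 1:1, so 190 per arm. Assumed, because the documents give neither: the share b already low before dosing, taken as equal in both arms by randomization, and the risk q of a low reading after the first dose in everyone else, here 25% (sparsentan) v 15% (irbesartan).

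- Ever low, as the SAP reads: b + (1 − b)q
- New cases over all patients: (1 − b)q
- The difference between arms is (1 − b)(qT − qC) for both.

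| b | Ever low | Ratio | Difference (points) | New cases over all | Ratio | Difference (points) |
|---|---|---|---|---|---|---|
| 0% | 25.0% v 15.0% | 1.67 | 10.0 | 25.0% v 15.0% | 1.67 | 10.0 |
| 5% | 28.75% v 19.25% | 1.49 | 9.5 | 23.75% v 14.25% | 1.67 | 9.5 |
| 10% | 32.5% v 23.5% | 1.38 | 9.0 | 22.5% v 13.5% | 1.67 | 9.0 |
| 20% | 40.0% v 32.0% | 1.25 | 8.0 | 20.0% v 12.0% | 1.67 | 8.0 |
| 30% | 47.5% v 40.5% | 1.17 | 7.0 | 17.5% v 10.5% | 1.67 | 7.0 |

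Among patients not low at baseline the difference is 10.0 points throughout.

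Precision: the standard error of the difference is √{[pT(1 − pT) + pC(1 − pC)]/190}.

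- b = 10%, ever low: √[(0.2194 + 0.1798)/190] = 4.6 points. New cases over all: √[(0.1744 + 0.1168)/190] = 3.9 points.
- b = 20%, ever low: √[(0.2400 + 0.2176)/190] = 4.9 points. New cases over all: √[(0.1600 + 0.1056)/190] = 3.7 points.

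The ever-low variance in an arm is the larger one when the two proportions sum to less than 1: b + 2(1 − b)q < 1, that is, q < 50%. The loss of precision therefore holds for new-case risks below one half.

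Other assumed risks give the same direction. With 20% v 10%, the ratio falls from 2.00 to 0.28/0.19 = 1.47 at b = 10% and 0.36/0.28 = 1.29 at b = 20%. With 40% v 25%, it falls from 1.60 to 1.42 and 1.30.

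If only values after the first dose count, and a share r of baseline-low patients is low again in both arms, ever low becomes br + (1 − b)q. With 25% v 15%, r = 50% and 80% give ratios of 1.49 and 1.42 at b = 10%, and 1.36 and 1.29 at b = 20%. The differences stay at 9.0 and 8.0 points.

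**The case against.** The strongest reply is that this is a reporting mismatch with many safeguards. The SAP does pre-specify low and high limits for the three main vital signs. Half of its criteria are referenced to baseline. Visit-wise change, an MMRM, orthostatic counts and treatment-emergent hypotension summaries (all, related and serious, on study and on treatment) also address low pressure. Protocol 12.8 makes safety summaries descriptive, so no test is at risk. The time frame could be programmed as post-baseline only. Use of on-study data is the stated default in SAP 10, so including Week 114 is a choice, not an oversight.

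Most of this stands and limits the point. It does not remove it. None of those outputs gives the new low reading at 100/60, and post-baseline programming still counts patients who were low and stay low. The SAP writes post-baseline elsewhere, including the opening sentence of 10.5, but not for these counts.

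The SAP cites Amendment 5, whereas the protocol supplied is Amendment 6. The stated reasons for Amendment 6 mention no change to vital signs, but Amendment 5's wording cannot be checked here.

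A further objection concerns the remedy. Dropping baseline-low patients from the absolute rows would lose information: a patient going from SBP 98 to 75 falls by 23 mmHg, misses the >30 mmHg row, and would then appear in no SBP threshold row. This stands, so the new-case row should be an addition.

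**Conclusion.** The omission is real and undeclared: the protocol promises vital-sign shift tables and the SAP does not specify them. As worded, the absolute-limit rows can count patients who were low before dosing. Any such patients pull the risk ratio toward 1, reduce the difference relative to the at-risk group and, for new-case risks below 50%, make the estimated difference less precise.

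A reader might infer that the arm difference is diluted outright, or that the plan as a whole understates drug-induced low blood pressure. The documents do not support either. The expected absolute difference equals that of new cases over all patients, and several other outputs bear on the same risk.

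The size is unknown. The ratios of 1.38 and 1.25 (against 1.67) rest on assumed baseline shares of 10% and 20%, assumed risks of 25% v 15%, and equal baseline shares in the two arms. If no patient is low at baseline there is no effect. The post-first-dose figures also assume the same r in both arms. The textual mismatch is firm; the numerical consequence is illustrative.

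**What to change.** In SAP 10.5:

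- Add shift tables by arm for SBP, DBP and heart rate, from baseline category to worst category after the first dose (lowest and highest value shown separately). Use the SAP's own limits as ranges: SBP ≤100, >100 to 180, >180 mmHg; DBP ≤60, >60 to 105, >105 mmHg; heart rate <45, 45 to 120, >120 per minute.
- State that the absolute-limit rows use only values after the first dose. Keep the all-patient count.
- Beneath each absolute-limit row, add one for patients who did not meet that limit at baseline, with their number as denominator.

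In SAP 5.4, record any part of Protocol 12.8.1 that will still not be done, such as classification of respiration rate and temperature.

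Blood pressure and heart rate are already collected at the scheduled visits, so the cost is SAP wording and a few extra descriptive tables. No clinical rule changes.

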### **12.8.2. Clinical Laboratory Tests**

Clinical laboratory parameters will be measured at baseline and postbaseline visits. Each continuous laboratory variable will be summarized in terms of changes from baseline by randomized treatment group.

Laboratory data will also be classified as low, normal, or high relative to the parameter's reference range. Laboratory abnormalities for each treatment will also be summarized using shift tables.

### **12.8.3. Adverse Events**

All AEs will be coded using MedDRA by System Organ Class and Preferred Term. AEs that begin after the first administration of study medication or existing AEs that worsen after the first dose of study medication are considered TEAEs. The number and percentage of patients reporting TEAEs will be summarized for each treatment group by MedDRA System Organ Class and Preferred Term, by severity, and by relationship to study medication. The number and percentage of patients reporting serious TEAEs, TEAEs leading to treatment discontinuation, TEAEs of interest, and cardiovascular-related TEAEs (including those resulting in death) will also be summarized for each treatment group by MedDRA System Organ Class and Preferred Term.

## **12.9. Other Analyses**

### **12.9.1. Prior and Concomitant Medications**

Concomitant medications and therapies will be coded using the World Health Organization Drug Dictionary. The incidence of prior and concomitant medications and therapies will be listed and summarized by randomized treatment group using frequency and percentage for the double-blind period and separately for the open-label extension period.

### **12.9.2. Pharmacokinetics**

Trough plasma levels for sparsentan and irbesartan will be summarized by visit using descriptive statistics.

## **12.10. Interim Analysis**

An unblinded interim analysis will be performed 36 weeks after randomization of at least 280 patients to evaluate the primary efficacy endpoint.

## **12.11. Analyses for the Open-label Extension Period**

Analysis of endpoints for the open-label extension period will be performed using the methods described in [Section 12.7](#), [Section 12.8](#), and [Section 12.9](#), as appropriate.

Efficacy and safety endpoints for the open-label extension period will be summarized using descriptive statistics and presented overall and by original randomized treatment based on the OLEFAS. Analyses using baselines other than Week 114 (eg, prior to the first dose of study medication in the double-blind period) may be explored; details will be provided in the SAP.

